Improving Ventilatory Capacity in Those with Chronic High Level SCI

Unique Protocol ID: 2016P002409
ClinicalTrials.gov ID: NCT05041322
Last Updated: 09/22/2021

Improving Ventilatory Capacity in Those with Chronic High Level SCI

I. BACKGROUND AND SIGNIFICANCE

Chemoreceptive regulatory feedback is crucial for precise ventilatory control, especially during exercise [1]. However, individuals with high-level SCI have a reduced chemoreceptive drive to breathe. Studies have shown lesser increases in minute ventilation and mouth pressure during hypercapnia in those with tetraplegia [2,3]. Peripheral factors rather than central factors appear to cause the reduction of the ventilatory response to hypercapnia [2]. This reduced ventilatory drive may have functional impact on exercise ventilation in patients with high level SCI [3] and enhancing ventilatory drive may improve exercise ventilation in high-level SCI.

Currently, there are no treatments to overcome these functional deficits that affect daily activity and exercise-based rehabilitation recovery. However, previous work in an animal model of SCI has found that that a serotonin agonist markedly increases respiratory responses to carbon dioxide. Treatment with a serotonin 5HT1A agonist effectively improved the ventilatory drive after both acute [4] and chronic [5] spinal cord injuries in rats. One potential mechanism is increased excitability of the ventral motoneurons that have survived the spinal cord injury. 5-HT1A receptors do exist on these neurons [6], and when activated, amplify the excitatory output [7]. Another mechanism resides at the intercostal and abdominal muscle afferents which influence supraspinal respiratory group neurons in the brainstem and motor output to the muscles of breathing [8,9]. Hence, serotonin agonists may act on neural pathways in the spinal cord responsible for transferring afferent information from intercostal muscles to supraspinal centers. Lastly, 5-HT1A receptors may also be involved in functional plasticity of neural respiratory pathways, in particular ipsilateral phrenic nerve activity [10] [11]. Up regulation of 5-HT1A receptors due to denervation supersensitivity could result in postsynaptic hyperresponsivity due to loss of descending input.

BuSpar/Buspirone is a serotonin 5HT1A agonist and used as an anxiolytic in humans. It does not cause sedation, has minimal effects on psychomotor performance or cognition, and has low threshold for abuse potential or dependence liability [12]. Prior studies have found Buspirone to be well tolerated [13,14]. It has been used safely in spinal cord injury, but not for respiratory purposes [15]. (Though there is one clinical trial in process: Role of Enhancing Serotonin Receptors Activity for Sleep Apnea Treatment in Patients With SCI.) However, Buspirone up to 60 mg daily has been used to treat disturbed respiratory rhythms in multiple sclerosis [16], brain cancer [17], and brainstem infarction [18]. Interestingly, in patients with COPD, a 14-day oral administration of buspirone (20 mg) found improved anxiety and depression as well as increased exercise tolerance with lesser sensations of dyspnea [19]. Hence, buspirone may offer a treatment to improve hypercapnic ventilatory drive. Given that oral administration of 30 mg results in peak plasma levels at one hour and that the average elimination half-life is about 2 to 3 hours, buspirone is an attractive and safe approach to exploring the ability to both acutely and chronically improve respiratory responses to exercise and/or hypercapnia exposure in those with high level spinal cord injury that limits breathing capacity.

HYPOTHESIS

We hypothesize that oral buspirone increases ventilatory drive (chemosensitivity) in response to progressive hypercapnia and in response to exercise in individuals with SCI,.

II. SPECIFIC AIMS

- 1) To determine if two weeks of administration of the serotonin agonist buspirone augments the ventilatory responses to hypercapnia in individuals with a spinal cord injury at T4 and above
- 2) To determine if two weeks of administration of the serotonin agonist buspirone augments the ventilatory responses to exercise in individuals with a spinal cord injury at T4 and above

III. SUBJECT SELECTION

Inclusion criteria

Individuals with chronic high-level SCI

Aged 18 to 50 years

Medically stable with SCI at neurological level \geq T4 with American Spinal Injury Association grade A or B or C.

Subjects must be able to perform arm crank exercise

Exclusion criteria

Cardiomyopathy; significant arrhythmias; blood pressure $>140/90$ mmHg; coronary disease; diabetes; other neurological disease; renal disease; cancer; recent weight change \geq 15 pounds; regular use of tobacco; intrathecal baclofen pump; grade 2 or greater pressure ulcers at erlevant contact site; peripheral nerve compressions or rotator cuff tears that limit the ability to exercise; history of bleeding disorder; current use of cardioactive, tricyclic antidepressants (amitriptyline, timipramine), other sedating agents; suicidal ideation; pregnant and/or breastfeeding women.

In addition, subjects must have no known hypersensitivity to buspirone hydrochloride and must not be taking a monoamine oxidase inhibitor. Subjects taking midodrine to treat hypotension will be allowed to participate in this study.

IV. SUBJECT ENROLLMENT

The Principal Investigator who is a Doctoral level physiologist with over 20 years of experience in performing these types of physiologic studies in humans will obtain consent during the first visit to the laboratory. Participants will be sent the consent form at least a week in advance so they have ample time to read and ask questions. Participants are encouraged to ask questions and are reminded that participation is strictly voluntary and will not affect their current or future care at Spaulding Rehabilitation Hospital or any of its affiliates.

V. STUDY PROCEDURES

Study design

A double-blind placebo controlled cross-over study in 20 individuals with high-level SCI will be performed to compare ventilatory responses after administration of placebo or 30 mg buspar. Ventilatory responses to a CO₂ rebreathing test and a bout of moderate to high intensity exercise will be assessed. In addition, an evaluation of sleep quality will be performed prior to, and following each drug phase.

Specifically, after two weeks of daily administration of buspar (dosing: starting at 15 mg 1 time a day for 2 days and increasing to 30 mg (15 mg in the morning and 15 mg at night) or placebo.

Subjects will also taper off the full dose of buspar by taking Buspar (15mg) 1 time a day for 2 days at the end of the two weeks. Ventilatory responses to a CO₂ rebreathing test, a bout of moderate to high intensity exercise, and sleep will be assessed again at the end of each two weeks phase.

Detailed procedures

Once recruited for the study, the volunteers will visit the laboratory for a health screening session to further determine eligibility, obtaining informed consent, detailed health history, and set-up for an at home sleep over night evaluation. The following da a three-hour session (Visit 1) includes resting pulmonary function test, resting heart rate and blood pressure, height and weight, as well as a baseline CO₂ rebreathing test and a maximal incremental arm crank exercise test to determine maximal workload and aerobic capacity.

[figure not shown]
After volunteers complete the screening process, they will return for two visits to investigate the effect of buspirone or placebo on ventilatory responses (cross-over design, please see Figure 1).

These two study visits will take approximately 3 hours to complete and will be 14 days apart.

The sessions will be similar to the initial sessions but with a resting pulmonary function test and blood pressure preceding the CO₂ rebreathing and arm-crank tests. Following each of these segments an over night sleep assesment will also be performed.

The study sessions will take place at Spaulding Hospital Cambridge under the direct supervision of Cardiovascular Research Laboratory with a responsible physician on site, aware that the exercise session is taking place and readily available via pager or telephone if complications arise. This medical coverage falls into the "Physician Coverage" category as per the approved Spaulding Rehabilitation Hospital Policy and Procedure "General Safety Precautions and Procedures for the Conduct of Human Research."

Figure 1: Study schema

Pre-screening procedures

All study subjects will be preliminarily screened over the telephone to ensure that they meet preliminary eligibility requirements. Subjects who meet preliminary eligibility criteria and are interested in participating will be sent the informed consent letter at least one week before the first visit.

Screening & at home sleep evaluation

Informed consent will be obtained at Spaulding Rehabilitation Hospital, Cambridge. Subjects will be screened to ensure they meet preliminary eligibility criteria. All subjects will undergo a clinical interview to determine the presence of any medical disorders.

The following study assessments will be completed:

- Sleep Evaluation

Visit 1: Baseline Evaluation Visit

The following study assessments will be completed:

- Height and Weight

- Resting blood pressure and heart rate
- Pulmonary function test
- CO₂ rebreathing test
- Maximal arm-crank exercise test

Visit 2 & 3: Laboratory Testing Visit

The second and third laboratory visits will be separated by fourteen days. All subjects will be instructed to abstain from vigorous exercise for 2 days prior to avoid muscle fatigue as well as autonomic and neuroendocrine effects of exercise, and instructed to refrain from caffeine and alcohol for the previous 24 hrs.

Distribution of Study Medication at the end of visit 1 and 2

After initial screening testing measures are complete, study medication (Buspar/Placebo) will be distributed to all volunteers by a study physician. Participants will be instructed as to how to take the medication dose. The initial dose of buspirone will be 15 mg daily (for two days) and will be increased by 15 mg to a dose of 30mg/day (15 mg in the morning and 15 mg iat night) with a 2-day 15 mg daily taper at the end of the two weeks.

Follow-up between visit 3 1-2 and 4 2-3: Adverse Event Monitoring (Telephone) day

Study staff will check in with study participants over the telephone at one week intervals to monitor any side effects or adverse events of the medication. If subjects are experiencing intolerable side effects, they will be taken off of the medication while completing the remaining study procedures. Participants will be informed that they may call study staff directly to report any side effects or adverse events at any time during the study.

Parameters to be measured

- Resting blood pressure and heart rate
- Pulmonary function test
- CO₂ rebreathing test
- Arm-crank Maximal exercise test
- Sleep Evaluation

Measurements

1) Pulmonary function test and resting blood pressure

Standard measurement of resting brachial arterial blood pressure and heart rate (electrocardiogram) will be performed.

All subjects will performed standard spirometry for spinal cord injury, as previously described [20]. The same technician will test all subjects. Subjects will be seated with belts or pant waists loosened and with a nose clip. The maneuver will be demonstrated, and instructions will be given to inhale completely and “blast” the air out. The subject will be encouraged to exhale maximally and sustain the effort at least 6 sec or longer, if possible depending on the ability and willingness of the subject to continue. The volume-time curve will be recorded on a kymograph, and the flow-volume loop will be electronically displayed for review. An acceptable effort will be a minimum exhalation time of 6 sec with a rapid start and a well-defined early peak in flow that is smooth and continuous. Three acceptable efforts will be obtained.

2) CO₂ rebreathing test

We will use the Duffin's Modification of the Read-rebreathing method from a bag containing 93-95% O₂ [to suppress peripheral chemoreceptor activity] and 5% CO₂, as previously described in the literature [21]. Subjects will be on a mouthpiece and wearing nose clips. Subjects will be coached to hyperventilate in room air for ~5 min. Then, they will be asked to exhale below functional residual capacity and then switched to the rebreathing bag for rebreathing ~95% O₂ and 5% CO₂. The PCO₂ measured at the mouth will approximate the PCO₂ at the level of the chemoreceptors. Rebreathing will continue until end-tidal PCO₂ (PETCO₂) reaches 55 mmHg (or 7.5% at a barometric pressure of 755 mmHg) and will be terminated if the subject feels that he or she cannot continue. Minute ventilation, PETCO₂, tidal volume, inspiratory time, expiratory time and respiratory frequency will be measured.

3) *Maximal incremental arm crank exercise*

Subjects will perform arms crank exercise with increasing power output every 1 to 2 minutes until volitional exhaustion. Online computer-assisted open circuit spirometry will be used to determine O₂ consumption, CO₂ production, and respiratory exchange ratio. Expired O₂ and CO₂ gas fractions will be measured with a paramagnetic O₂ and infrared CO₂ analyzers. Ventilation will be measured via a Hans Rudolph 3813 pneumotachograph. To ensure attainment of maximal exercise capacity, at least 3 of the following criteria will be met: 1) O₂ consumption plateaus despite increasing workload, 2) respiratory exchange ratio equals or exceeds 1.10 at end exercise, 3) peak lactate greater than 7.5 mmol/L, 4) perceived exertion is rated at least 17 on the Borg scale of 6-20. Immediately after exercise, subjects will have a finger tip pricked with a safety lancet to obtain a drop of blood to measure peak lactate levels.

4) *Sleep Evaluation*

An in-home Single night Polysomnography (PSG) using the type 2 level NOX A1 (NoxMedical) device will provide quantitative assessments of levels of overnight hypoxemia, apneas and hypopneas, sleep stage distributions, and will provide quantitative data on snoring. The recording montage will include five, self-applied frontal electroencephalogram electrodes, thoracic and abdominal respiratory inductance plethysmography, airflow via nasal cannula, ECG (4 electrodes on torso), leg movement sensors, finger pulse oximetry, and snoring microphone. Participants will be instructed on self-application of all sensors before bedtime, using simple pictorial aides and will be provided a phone number of a staff member to contact should any problems in set-up be encountered. Instructions will be given on how to move about with the recording unit, and how to self-remove the electrodes and sensors. The NOX A1 PSG units will be returned by to the study personnel on the following day or at the participant's earliest convenience.

PSG studies will be downloaded from collection equipment to the SRC computer using commercial software. Scoring of the PSGs will be made by a trained member of the study group through visualizing each epoch on a high resolution computer monitor using specialized software. Respiratory events, sleep stages and EEG (cortical) arousals will be scored according to standard guidelines.

VI. STATISTICAL ANALYSIS

Sample Size

Sample size is based on previous data from our laboratory. We used mean and standard deviation of peak ventilation during arm crank exercise in individuals with low and high level SCI (Battikhia

et al. 2014). We assume that Buspirone would increase peak ventilation by 35% in humans, though to our knowledge, there is no reference available on the ventilatory effect of Buspirone in individuals with SCI. Thus, with a highest SD of 8.3 L/min, we expect that peak ventilation during arm crank ergometer exercise in high level individuals with SCI will be increased from 31.3 L/min at baseline to 42.1 L/min with buspirone, as compared with no change in the placebo-controlled group. With an a p level of 0.05 and a power of 80%, the sample size calculation indicates that we need at least 9 participants per group. Anticipating 10% drop out, we will need 10 participants per group, for a total of 20 participants.

Statistics

These projects will employ typical/appropriate statistical approaches to compare changes within and between groups. Statistical significance will be set at 0.05, and power at 80%. Statistical tests, conformity of the data to required statistical assumptions (e.g., normal distribution) will be verified using standard methods (e.g., Kolmogorov-Smirnov statistics and Q-Q plots). If assumptions for parametric tests do not hold, non-parametric alternatives will be employed. Correlations between variables will be assessed when necessary by Pearson's or Spearman's coefficient depending on the normality of the variables. If significant relations are found, appropriate regression analyses will be employed.

VII. RISKS AND DISCOMFORTS

Moderate risks are associated with exercise (arm-crank) testing. Some discomfort and feeling of fatigue will be experienced during these tests. There are other risks associated with these tests including abnormal blood pressure responses, fainting, irregular, fast or slow heart rhythm, and in rare instances, heart attack, stroke, or death. Wearing the mouthpiece during the arm-crank exercise testing may cause feelings of claustrophobia. Exercise testing may also induce some muscle or joint discomfort when and could result in tendonitis and/or musculoskeletal injuries. There is some discomfort with the lancet used on the finger for lactate measurement.

There are no known risks associated with the EKG or blood pressure measurement. A subject must remove or lift up his or her shirt and have sticky patches applied to the chest for the electrocardiogram (EKG). In some cases, chest hair may have to be shaved where the EKG patches are placed. If an abnormality is identified on an EKG, the subject would be given this information and referred to his or her own doctor for further evaluation. Subjects may feel lightheaded or short of breath during the pulmonary function tests, there is also a slight chance that individuals become dizzy. The CO₂ re-breathing may cause slight lightheadedness in some people; however, this can be reversed almost immediately by switching them back to room air.

Buspar: BuSpar(r) (Buspirone HCl, USP) is an antianxiety agent that is not chemically or pharmacologically related to the benzodiazepines, barbiturates, or other sedatives/anxiolytics drugs. The mechanism of action of Buspirone is unknown but it does not exert anticonvulsant or muscle relaxant effect and it has no prominent sedative effect. Common side effects include: drowsiness, fatigue, dry mouth, or an increase in nightmares or dreams. Rare, but serious side effects include: an allergic reaction (difficulty breathing; hives; swelling of lips, tongue or face); chest pain or an irregular heartbeat; headache, dizziness, lightheadedness, slurred speech, confusion or blurred vision; numbness or tingling in hands, feet, arms or legs; depression; or uncontrolled movements of arms, legs tongue or lips.

Polysomnography: Sleep may be disturbed during the polysomnography study causing next day sleepiness. Skin irritation or discoloring may occur under adhesives used to attach the study sensors.

VIII. POTENTIAL BENEFITS

This research may help physicians and scientists to better understand how the interaction between a serotonin agonist pharmacological agent (buspar) and minute ventilation during hypercapnia and exercise. Although it is possible volunteers may better tolerate CO₂- rebreathing and exercise with buspar, this is a pilot study and further work may be necessary to establish the beneficial effects of buspar for those with high level spinal cord injury.

IX. MONITORING AND QUALITY ASSURANCE

The research coordinator will be responsible for monitoring the completeness of all data and source documents. The Principal Investigator will monitor the informed consent procedures in accordance with the Informed Consent Compliance Checklist of Partners HealthCare Systems HRQIP. The subjects data/protocol adherence will be monitored by the research coordinator at each step in the study including. Checklists and note pages are used to note any deviations or omissions from the protocols. All spinal cord injured participants will be asked the "Pre-Study Screening" questions before every visit. The Cardiovascular Research Laboratory Medical Emergency Safety Plan will be followed in the case of an adverse medical event. Any clinical/health related issues would be immediately presented to the subject (i.e. abnormal EKG, blood chemistries, etc) to determine appropriate notification (ie. current physician or appropriate specialist) Based on the seriousness of the situation a physician may be contacted to provide clinical guidance on the appropriate course of action.

Serious adverse events will be reported to the IRB via phone, email, or fax. The principal investigator will follow this with a full written report using the PHRC Adverse Event Form within 10 working days. If a mild or moderate adverse event occurs that is definitely, probably, or possibly related to the study, a written report will be sent to the IRB within 20 working days. All other events will be summarized in a progress report at continuing review.

X. REFERENCES

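### The outcome tests fall on or just after a two-day taper with no set time from last dose, so drug level at testing can vary widely and a null result would be hard to read

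*Combined protocol and SAP*

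**What the plan says.** Section V, Study design, sets out to "compare ventilatory responses after administration of placebo or 30 mg buspar". The full dose is split as "15 mg in the morning and 15 mg at night", reached after two days at 15 mg once daily. Participants come off it "by taking Buspar (15mg) 1 time a day for 2 days at the end of the two weeks", and the paragraph on distribution of study medication repeats this: the course ends "with a 2-day 15 mg daily taper at the end of the two weeks". Neither place says whether the single taper dose is the morning or the night one.

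On testing, Study design says that the response to CO2 rebreathing, "a bout of moderate to high intensity exercise, and sleep will be assessed again at the end of each two weeks phase". It also places a sleep evaluation before and after each drug phase. Detailed procedures says of Visits 2 and 3: "These two study visits will take approximately 3 hours to complete and will be 14 days apart". An overnight sleep study follows each. Study drug is handed out at the end of Visits 1 and 2. The schema is referred to ("cross-over design, please see Figure 1") but is not shown in our copy.

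The instructions before Visits 2 and 3 cover vigorous exercise, caffeine and alcohol. They do not mention study drug. Participants are to be told how to take their medication, but the content of that advice is not given. Section I states that a 30 mg oral dose peaks at one hour and that the half-life averages about 2 to 3 hours.

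**The concern.** With a half-life this short, the level at the test depends mostly on when the last dose was taken, and the plan leaves that open. It controls exercise, caffeine and alcohol before the visit, but not the drug being tested. The taper then places the tests in the two days when one of the two daily doses has been dropped, or just after them.

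Two things are at stake. Exposure at the test may differ between participants, and for one participant between the laboratory tests and the sleep study. And if the tests are done with little drug present, a null result could mean either that 30 mg/day has no effect on ventilation or that there was little drug to act. Section I gives the one-hour peak and short half-life as reasons why buspirone suits the study of both acute and chronic effects, so the level at testing matters on the plan's own rationale.

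**Working it through.** **Where the tests fall.** A two-week phase with two days of build-up and two of taper is 2 + 10 + 2 = 14 days, so 10 days are at 30 mg/day. Call Visit 2 day 0 and Visit 3 day 14. If second-phase dosing starts on day 0, the 14 dosing days are 0 to 13 and Visit 3 is the day after the last taper dose. If it starts on day 1, they are days 1 to 14 and Visit 3 is the second taper day. Either way, Visit 3 is on or just after the taper. The same holds for Visit 2 if it closes a two-week first phase.

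**Inputs.** Half-life h = 2 or 3 h and peak at 1 h (section I); each dose 15 mg (section V). Assumed: first-order decay and full doses 12 h apart. The plan gives no figure for exposure at the test, so there is none to reproduce.

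**Formulas.** Share left after 12 h: r = 0.5^(12/h) = 0.0156 (h = 2) or 0.0625 (h = 3). Share left after 24 h: r² = 0.00024 or 0.0039. Steady-state factor: 1/(1 − r) twice daily, 1/(1 − r²) once daily. Their ratio, once daily to twice daily, is 1/(1 + r).

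**Laboratory tests**, as a share of the level at the same clock time on 30 mg/day with the morning dose taken:

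| Situation | Formula | h = 2 h | h = 3 h |
|---|---|---|---|
| 30 mg/day, morning dose not yet taken | r | 1.6% | 6.3% |
| Taper, dose taken that morning | 1/(1 + r) | 98% | 94% |
| Taper, last dose the night before | r/(1 + r) | 1.5% | 5.9% |
| Taper, last dose the previous morning | r²/(1 + r) | 0.02% | 0.4% |

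**Which part drives the range.** At full dose, the unset dose time alone gives a spread of 1/r = 64- or 16-fold. At the same last-dose time, the taper lowers the level only by the factor 1 + r, that is 1.02- to 1.06-fold, because each dose is 15 mg in both schedules. It adds a further (1 + r)/r = 65- or 17-fold only if the taper dose is a morning dose and none has been taken on the test day.

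**Sleep study**, as a share of the level just after a full-dose night dose: taper dose that night, 94-98%; taper dose that morning, 1.5-5.9%; last dose the night before, 0.02-0.4%.

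**Within a visit.** Over the 3 h after the peak the level falls to 0.5^(3/h) = 35% or 50%.

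**Check with absorption.** A one-compartment model peaking at 1 h (absorption rate 2.19 or 2.68 per h), with tests 1 to 4 h after the usual morning dose time, gives 1.6-6.8%, 94-98%, 1.5-6.4% and 0.02-0.4% for the four rows of the table. The fall over 3 h is then to 42-54%.

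**The case against.** The strongest reply is that plasma level at the test is not the stated target. Both aims speak of two weeks of administration, section I includes a plasticity mechanism, and the 30 mg can be read as a label for the whole titrated course. This stands: testing after a taper does not contradict the aims, and an effect that outlasts the drug would still be tested.

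Second, participants are prescribed a morning dose at full dose and nothing tells them to withhold it, so many may arrive with drug on board. That is fair. But nothing ensures it, the taper may remove that dose, and no time is fixed or recorded. The unstated dosing advice may cover timing; if so, it belongs in the protocol.

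Third, the lowest laboratory figure, 0.02-0.4%, needs several unfavourable conditions together: testing on or after the taper, a morning taper dose, and none taken that day. That also stands; it is the end of a range, not an expectation.

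A reader might infer that the plan leaves the order of taper and tests wholly open, or that the taper runs into the second phase. The written text does not support this. It puts the taper inside the two weeks, the tests at their end and the sleep evaluation after the phase. Figure 1 may show the order differently, but could not by itself supply the missing dose time unless it gives one.

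**Conclusion.** The concern holds in a limited form and is worth fixing. As written, the outcome tests fall on or just after the taper, and no time from last dose to test is set. The unset dose time is the main driver: testing before rather than after the morning dose leaves about 2-6% of the level. The taper contributes mainly by removing one of the two daily doses, which also bears on the sleep study.

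Two stronger readings are tempting. One is that tapering by itself substantially lowers exposure at the test; at the same last-dose time it lowers it by only 2-6%. The other is that the trial would be uninformative or lose a known amount of power; the documents do not relate drug level to ventilation, so the size of any lost effect cannot be derived. The harm is variable exposure and a null result open to two explanations.

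This rests on the stated half-life, first-order decay, doses 12 h apart, and the written schedule in the absence of Figure 1. Confidence is medium for that last reason.

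**What to change.** **Minimum.** Have participants take a 15 mg study dose (drug or placebo) at a fixed time before the laboratory tests, for example about 1 h, the same at Visits 2 and 3. Record the dose time and when the tests start. The visit must then fall on a dosing day. State where the tests lie relative to the taper and which daily dose the taper keeps. This costs protocol wording and a few recorded times per visit.

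**Preferred.** Keep participants on 30 mg/day through the test day and the night dose before the sleep study, taper afterwards, and start second-phase drug only after the taper. For example, test on days 14 and 30, with tapers on days 15-16 and 31-32. Each test then follows two full weeks of drug. The cost is 32 − 28 = 4 more days per participant, visit spacing of 30 − 14 = 16 days instead of 14, and 2 more days at 30 mg/day in the buspirone phase (12 instead of 10). Dispensing must change too: at Visit 2 participants would still be finishing the first supply, so the second must be issued later or clearly marked with its start date. No extra participants or test procedures are needed.

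**If post-taper testing is intended.** Still fix and record the dose time, and state the conclusion as the effect after a two-week course that ended in a taper. That choice is for the investigators.

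### As written, the 2-day taper to 15 mg/day and the end-of-phase tests coincide, so buspirone may be tested at half the stated daily dose; separately, no dose-to-test time is fixed

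*Combined protocol and SAP*

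**What the plan says.** All references are to the combined protocol and SAP.

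- **Dose compared.** Section V, Study design, describes a crossover "to compare ventilatory responses after administration of placebo or 30 mg buspar". The dose starts at 15 mg once daily for two days and then rises to 15 mg in the morning and 15 mg at night.
- **Taper.** The same subsection has participants come off the full dose by "taking Buspar (15mg) 1 time a day for 2 days at the end of the two weeks". The medication subsection repeats this: "with a 2-day 15 mg daily taper at the end of the two weeks".
- **Tests.** The sentence after the taper in Study design says that CO₂ rebreathing, exercise and "sleep will be assessed again at the end of each two weeks phase". Detailed procedures adds an overnight sleep assessment after each segment.
- **Calendar.** "The second and third laboratory visits will be separated by fourteen days", and drug is handed out under the heading "Distribution of Study Medication at the end of visit 1 and 2".
- **Pre-visit rules.** Participants avoid vigorous exercise for two days and are "instructed to refrain from caffeine and alcohol for the previous 24 hrs". They are to be told how to take the medication, but the content of that instruction is not given. No dose time relative to the tests appears, and the taper text does not say whether the single daily dose is a morning or a night dose.
- **Pharmacokinetics.** Section I gives a plasma peak at one hour and an elimination half-life of about 2 to 3 hours.

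**The concern.** Two events are assigned to the same point in the phase: stepping down to half the daily dose, and measuring the outcomes. No sentence puts one before the other. If sites follow the text literally, participants are measured after half the daily dose has been withdrawn, while the stated contrast is 30 mg against placebo. A small or null difference would then be harder to interpret as evidence about 30 mg/day.

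A second gap is independent of the taper. For a drug that peaks at one hour and has a half-life of 2 to 3 hours, the plasma level during a test depends heavily on when the last dose was taken, and the plan leaves that open. In a crossover of 20 people this is avoidable variation between participants.

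**Working it through.** The plan gives no figure of its own on this point. The sample-size calculation has no dose term and is not affected. The check is a dose calendar, followed by first-order decay at the protocol's half-life.

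**1. Calendar as written.** Count day 1 as the first dosing day.
- Days 1–2 at 15 mg, days 3–12 at 30 mg, days 13–14 at 15 mg: 2 + 10 + 2 = 14 days.
- Total drug: 2×15 + 10×30 + 2×15 = 360 mg.
- Daily dose at an end-of-phase test: 15/30 = 50% of the stated dose.

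This schedule satisfies every stated timing.

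**2. Could the taper follow the tests?** The answer depends on the sequence.
- *Buspirone first:* phase 2 medication is handed out at Visit 2, and Visit 3 comes 14 days later. A taper after the Visit 2 tests would overlap the first two days of the placebo phase, or phase 2 would have to start late and run short of two weeks. Neither is described.
- *Buspirone second:* Visit 3 is the last visit, so a taper afterwards is possible. The telephone checks, headed "Follow-up between visit 3 1-2 and 4 2-3: Adverse Event Monitoring (Telephone) day" (read here as between Visits 1 and 2 and between Visits 2 and 3), would not cover it.

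**3. Dose-to-test time, with or without a taper.** Assume one-compartment linear kinetics, a peak at 1 h, and 12 h between the morning and night doses. The fraction of peak left t hours after a dose is 2^(−(t−1)/h), with half-life h.

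| Time after dose | h = 2 | h = 3 |
|---|---|---|
| 12 h | 2^(−11/2) = 2.2% | 2^(−11/3) = 7.9% |
| 14 h | 2^(−13/2) = 1.1% | 2^(−13/3) = 5.0% |
| 24 h | 2^(−23/2) = 0.03% | 2^(−23/3) = 0.5% |

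The ratio of the 1 h level to the 12 h level is 1/0.0221 = 45 (h = 2) or 1/0.0787 = 13 (h = 3). On twice-daily dosing the longest gap between doses is 12 h. On the once-daily taper it is 24 h.

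**4. What the taper itself does to the laboratory tests.** Each dose is 15 mg in both regimens. The steady-state peak on once-daily dosing relative to twice-daily dosing is (1 − 2^(−12/h)) / (1 − 2^(−24/h)):
- h = 2: 0.9844/0.9998 = 0.98
- h = 3: 0.9375/0.9961 = 0.94

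If a taper dose is taken 1 h before the test, 94% to 98% of the peak is kept and only the daily dose is halved.

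**5. Sleep night.** The full regimen includes a 15 mg night dose. If the taper dose is taken in the morning, 1.1% to 5.0% of peak is left at an assumed bedtime 14 h later.

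**The case against.** The order of taper and tests is inferred. Coming off the drug at the end of two weeks can also mean once the two weeks are over, and Detailed procedures refers the reader to Figure 1, which is not shown here and may settle the matter. A reader might infer that the protocol states that buspirone is tested at 15 mg/day. It does not. That is the natural literal reading, and no more.

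A reader might also infer that neither phase has room for a later taper. That holds only for phase 1. Even there an overlapping taper is not excluded, and it would end about 14 − 2 = 12 days before Visit 3, far beyond the drug's half-life. What stands is that the overlap, and how it would be blinded, are not described.

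A third tempting inference is that the taper causes the 13- to 45-fold spread in plasma level. It does not. That spread comes from unfixed dose timing, and a well-timed taper dose nearly keeps the peak.

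Nor do the documents show any loss of effect or power. They give no dose-response. Both Specific Aims name two weeks of administration and no dose, and Section I lists functional plasticity among the possible mechanisms, so the level at the hour of testing may not govern the effect. Participants would also have had 10 full-dose days before the taper.

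Finally, dosing instructions are promised and might set a time. Even so, the protocol itself does not fix one, and nothing in the readable text puts the tests ahead of the taper.

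**Conclusion.** The point holds as a weakness in the readable text, with medium confidence because Figure 1 could show a different order. Followed literally, the schedule puts the buspirone tests and the sleep night on or just after 15 mg/day, 50% of the stated daily dose, after 10 days at full dose. For the laboratory tests the consequence may be small if a dose is taken about an hour beforehand, but nothing ensures that. The sleep night is more exposed if the single taper dose is taken in the morning, although sleep is in neither Specific Aim.

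The missing dose-to-test interval is the firmer half of the point, because it does not depend on where the taper falls. The 13- to 45-fold range rests on the protocol's own peak time and half-life, linear one-compartment decay, and a comparison of 1 h with 12 h. The size of any lost effect is unknown. It would go too far to say that a null result could tell us nothing about 30 mg/day. The fair statement is that the result would be harder to attribute to that dose than it needs to be.

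**What to change.** Do the Visit 2 and Visit 3 tests and the following sleep night while participants still take 30 mg/day or matched placebo. Fix the time of testing after the morning dose, for example 1 h, the protocol's peak time. Because a visit lasts about 3 h, between 3/3 = 1 and 3/2 = 1.5 half-lives, state the time for each test and keep it the same at both visits. Run the 2-day taper afterwards, matched in the placebo phase, and start phase 2 when it ends. Phase 2 medication can still be handed out at Visit 2 with a stated start date.

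- **Preferred:** test on day 14, taper on days 15–16, start phase 2 on day 17, and hold Visit 3 on day 16 + 14 = 30. This keeps the two weeks of dosing named in the aims. Visits 2 and 3 are then 30 − 14 = 16 days apart, two more than now. Buspirone per participant is 2×15 + 12×30 + 2×15 = 420 mg, which is 60 mg more than 360 mg.
- **Alternative:** test on day 12, taper on days 13–14, start phase 2 on day 15, and hold Visit 3 on day 14 + 12 = 26. The 14-day visit gap, the 360 mg total and the 10 full-dose days are kept, but the plan must then describe 12 days of dosing before the test.

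Either option needs a protocol amendment and one added telephone check for the taper after Visit 3. Neither adds a laboratory visit or a sleep night. If Figure 1 already puts the tests before the taper, the text should be brought into line with it and the dose-to-test time added.
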